To date, there is no publication comparing biologics for the treatment of Ps that inhibit IL-23 (specifically IL-23p19) vs. those that inhibit IL-17; thus expectations of efficacy between these 2 types of new biologics are not well delineated. Studies of ixekizumab suggest equal, if not superior ability compared to guselkumab to achieve PASI 90 (as shown in the VOYAGE studies). Ixekizumab also demonstrated a high percentage of patients achieving PASI 100, and a rapid onset of skin improvement after administration of ixekizumab (UNCOVER). Comparing these 2 classes of biologics in a study, in which both are tested with the same endpoints and measured at the same time, will provide important information to clinicians trying to determine which drug class is the best for a given patient. The purpose of this study is to compare efficacy and safety, as well as rapidness of efficacy, of ixekizumab and guselkumab.

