The primary analyses for the continuous efficacy and health outcome variables will be performed using mixed effects model for repeated measures (MMRM) analysis. The model will include treatment, pooled site, baseline value, visit, treatment-by-visit interaction and baseline value-by-visit as fixed factors. A secondary analysis for continuous efficacy and health outcomes variables will be made using analysis of covariance (ANCOVA) adjusting for pooled site and baseline value.

Fisher's exact test will be used for all AE, baseline, discontinuation, and other categorical safety data. Continuous laboratory values will be analyzed by an ANCOVA with treatment and baseline value in the model.

Any change to the data analysis methods described in the protocol will require an amendment ONLY if it changes a principal feature of the protocol. Any other change to the data analysis methods described in the protocol, and the justification for making the change, will be described in the clinical study report (CSR). Additional exploratory analyses of the data will be conducted as deemed appropriate.

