5.3. Determination of Sample Size

Approximately 960 patients will be randomized at a 1:1 ratio to ixekizumab and guselkumab. With 480 patients per treatment group, this study will have 98% power to test the superiority of ixekizumab to guselkumab for a 100% reduction in the Psoriasis Area and Severity Index (PASI 100) at Week 12. The following assumptions were used for the power calculation response rate at Week 12: 35.3% and 23.0% for the ixekizumab and guselkumab groups, respectively. A 2-sided Fisher's exact test at a significance level of 0.05 is assumed. This study is also powered at 95% to test the superiority of ixekizumab for PASI 100 at Week 24, assuming the response rate of ixekizumab and guselkumab at 56% and 44%, respectively. These assumptions are based on the ixekizumab and guselkumab clinical studies in psoriasis (Griffiths et al. 2015; Gordon et al. 2016; Blauvelt et al. 2017; Reich et al. 2017).

For the non-inferior test of PASI 100 at Week 24, a non-inferiority margin of -11.4% is considered sufficiently small to be clinically unimportant difference in outcome between guselkumab and ixekizumab. This non-inferior margin is based on a 70% retention rate approach assuming a placebo response rate of 6.0% at Week 24 observed in a phase 2 study (Deodhar et al. 2018). The sample size of 480 patient per treatment group provides >99% power to test the non-inferiority.

6. A Priori Statistical Methods

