When the MMRM model is used, the covariance structure to model the within-patient errors will be unstructured. The restricted maximum likelihood (REML) will be used. The Kenward-Roger method will be used to estimate the denominator degrees of freedom. The Newton-Raphson with ridging optimization technique will be used to aid with convergence. If the unstructured covariance matrix results in a lack of convergence, the heterogeneous Toeplitz covariance structure, followed by the heterogeneous autoregressive covariance structure, followed by the compound symmetric structure will be used. The first structure to yield convergence will be used for inference. Type III tests for the least squares (LS) means will be used for the statistical comparisons; the corresponding 95% CIs will also be reported.

When the ANCOVA model is used, missing data will be imputed using the modified baseline observation carried forward (mBOCF). Type III sums of squares for the LS means will be used for the statistical comparisons; the 95% CI will be reported.

The Kaplan-Meier product limit method will be used to estimate the survival curves for time-to-event variables. Treatment comparisons will be performed using the log-rank test. Patients completing the Blinded Treatment Periods without event will be censored at the date of completion (that is, the date of the last visit in the Blinded Treatment Periods). Patients without a date of completion or discontinuation for the Blinded Treatment Periods will be censored at the latest non-missing date out of the following dates: date of last dose and date of last attended visit in the Blinded Treatment Periods.

Fisher's exact test will be used for all adverse event (AE), categorical baseline characteristics, discontinuation, and other categorical safety data. The continuous baseline characteristics will be analyzed using an analysis of variance (ANOVA) model with treatment as a factor. Continuous vital sign data and laboratory values will be analyzed by an ANCOVA with treatment and baseline value in the model. For condition/event that is gender-specific (as defined by the Medical Dictionary for Regulatory Activities [MedDRA]), the denominator and computation of the percentage will include only patients from the given gender.

Data collected at ETVs will be mapped to the next planned visit number for that patient. For by-visit summaries, only visits in which a measure was scheduled to be collected will be

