summarized. Unplanned/Unscheduled measurements will be excluded from the MMRM analysis. However, the data will still be used in other analyses; such analyses include, but are not limited to, shift analyses and mBOCF endpoint analyses.

All CIs and statistical tests will be 2-sided with an alpha-level of 0.05, unless specified otherwise.

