6.14.3.1. Special Safety Topics including Adverse Events of Special Interest

Safety information on special topics including AEs of special interest (AESI) will be presented by treatment. [Table RHCR.6.8](#) provides the definitions/derivations and analyses methods (including analyses, summaries and by-patient listings) of special safety topics including AESIs.

Potential AESIs will be identified by a standardized MedDRA query (SMQ) or a Lilly-defined MedDRA PT listing. Preferred terms within an SMQ will be classified as broad and narrow. In the Lilly-defined MedDRA PT listings, Lilly has provided the broad and narrow classification. The Lilly-defined broad terms are for a more sensitive search of potential events of interest and the Lilly-defined narrow terms are for a more specific search. Therefore, the summaries will include the classifications of broad term (same as pooling narrow and broad terms together) and narrow term.

In the event that the listing of terms or analysis changes for a special safety topic, it will be documented in the compound level safety standard (Program Safety Analysis Plan 2018) which will supersede this document; it will not warrant an amendment to the individual study SAP.

Fisher's exact tests will be used to compare the treatment groups for the safety population during the Blinded Treatment Periods.

Table RHCR.6.8. Definitions and Analyses of Special Safety Topics including Adverse Events of Special Interest

Special Safety Topic	Definition / Derivation	Analysis / Summary / Listing
Hepatic	
Hepatic AE analysis will include events that are potentially drug-related hepatic disorders by using the Medical Dictionary for Regulatory Activities (MedDRA) PTs contained in any of the following standardized MedDRA query (SMQ) or sub-SMQ as defined in MedDRA:
 
 • Broad and narrow terms in the Liver related investigations, signs and symptoms (20000008) • Broad and narrow terms in the Cholestasis and jaundice of hepatic origin (20000009) • Broad and narrow terms in the Hepatitis, non-infectious (20000010) • Broad and narrow terms in the Hepatic failure, fibrosis and cirrhosis and other liver damage (20000013) • Narrow terms in the Liver-related coagulation and bleeding disturbances (20000015) 	
Blinded Treatment Periods (Fisher’s exact test): TEAEs by PT within SMQ or sub-SMQ

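### Adverse events are compared between arms by Fisher's exact test with no confidence interval for the difference, so a non-significant result for an uncommon event says little

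*SAP*

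**What the plan says.** Protocol section 3.2 states the aim: "The purpose of this study is to compare efficacy and safety, as well as rapidness of efficacy, of ixekizumab and guselkumab".

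The method for categorical safety data is the same in both documents. Protocol section 10.3.1 says that Fisher's "exact test will be used for all AE, baseline, discontinuation, and other categorical safety data". SAP section 6.1.3 says that Fisher's "exact test will be used for all adverse event (AE), categorical baseline characteristics, discontinuation, and other categorical safety data". SAP section 6.14 repeats the choice for safety comparisons in general. Section 6.14.3.1 says, for the special safety topics, that Fisher's "exact tests will be used to compare the treatment groups for the safety population during the Blinded Treatment Periods", and the analysis column of Table RHCR.6.8 names that test for its between-arm comparisons.

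SAP section 6.14.2 has the adverse event tables show the number and percentage of patients by treatment. Injection-site reactions also get a count per 100 active injections, a duration and a time to onset. Neither document plans a risk difference with an interval for any adverse event category. The general sentence in SAP section 6.1.3, "All CIs and statistical tests will be 2-sided with an alpha-level of 0.05, unless specified otherwise", fixes the level of any interval that is produced but does not call for one here.

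For efficacy, Protocol sections 10.3.1 and 10.3.3.1 plan a 95% interval for the treatment difference in binary endpoints. SAP section 6.17.1 plans one for each efficacy subgroup category, and section 6.11.3 plans one for the Week 24 non-inferiority comparison.

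The sample size is justified on PASI 100 alone: "With 480 patients per treatment group, this study will have 98% power to test the superiority of ixekizumab to guselkumab" (SAP section 5.3). No expected rate, detectable difference or power is given for any safety event.

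**The concern.** For an uncommon event, a p-value above 0.05 can mean either that the two drugs are similar or that there were too few events to tell. Fisher's test alone does not separate the two. An interval does, because its upper end shows how large an excess the data still allow. The plan supplies that information for exploratory efficacy subgroups but not for serious infections, major cerebro-cardiovascular events or inflammatory bowel disease. What is at stake is the comparative safety statement of a head-to-head trial. The primary and major secondary efficacy conclusions are untouched.

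**Working it through.** **Inputs from the documents.** 480 patients per arm, 1:1 allocation, two-sided alpha 0.05 and Fisher's exact test (SAP sections 5.3 and 6.1.3). The safety population needs only one dose, so the anticipated 5% dropout (Protocol section 5.2) does not materially reduce it.

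**Inputs that must be assumed.** Event rates in each arm, because the documents give none. A range is shown.

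**Formula.** Exact power is the sum, over all pairs (x1, x2), of Bin(x1; 480, p1) × Bin(x2; 480, p2), counting only pairs whose two-sided Fisher p-value is at most 0.05.

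**Step 1: reproduce the plan's own figures.** For PASI 100 at Week 12, with assumed rates of "35.3% and 23.0% for the ixekizumab and guselkumab groups, respectively", the formula gives 98.6% against a stated 98%. For Week 24, 56% versus 44% gives 95.5% against a stated 95%. Both agree.

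**Step 2: apply the same formula to assumed adverse event rates.**

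| Scenario | Rates | Power |
|---|---|---|
| Doubling, base 3% or less | 0.5% vs 1% | 6% |
| | 1% vs 2% | 17% |
| | 2% vs 4% | 38% |
| | 3% vs 6% | 56% |
| Larger ratio, low base | 1% vs 4% | 84% |
| Doubling, base 5% or more | 5% vs 10% | 81% |
| | 10% vs 20% | 99% |
| 10-point difference, common event | 20% vs 30% | 94% |
| | 25% vs 35% | 91% |
| Smaller difference, common event | 5% vs 8% | 42% |
| | 10% vs 15% | 62% |
| | 20% vs 25% | 43% |

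The rate detectable with 80% power is 2.9% against 0.5% (ratio 5.8), 3.8% against 1% (ratio 3.8), 5.6% against 2% (ratio 2.8) and 9.9% against 5% (ratio 2.0).

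**Step 3: what an interval would add.** Take 10 versus 5 patients with an event. The rates are 10/480 = 2.08% and 5/480 = 1.04%, so the difference d is 1.04 points. The Wilson 95% limits are 1.14% to 3.79% and 0.45% to 2.42%. Newcombe's method combines them:

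- lower limit = d − √[(2.08 − 1.14)² + (2.42 − 1.04)²] = 1.04 − 1.67 = −0.6 points
- upper limit = d + √[(3.79 − 2.08)² + (1.04 − 0.45)²] = 1.04 + 1.81 = +2.9 points (2.85 before rounding)

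The same method on other assumed counts, 480 per arm:

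| Patients with event | Fisher p | 95% interval (points) |
|---|---|---|
| 2 vs 0 | 0.50 | −0.4 to +1.5 |
| 5 vs 2 | 0.45 | −0.6 to +2.0 |
| 10 vs 5 | 0.30 | −0.6 to +2.9 |
| 60 vs 48 | 0.26 | −1.5 to +6.5 |
| 5 vs 0 | 0.062 | +0.05 to +2.4 |

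The first four rows are clearly non-significant, yet they allow excesses of about 1.5 to 3 points for rare events and more than 6 points for a common one. The last row shows that an interval and Fisher's test can disagree at sparse counts.

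**The case against.** The strongest reply is that the reader is not left with bare p-values. Counts and percentages by arm are tabulated, so a crude difference is visible and anyone can compute an interval. There are also severity tables, patient listings, exposure in patient-years, shift tables and external adjudication of cerebro-cardiovascular and bowel disease events. This stands as far as it goes: the gap is in the planned inference, not in the description of the data.

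The objectives tables contain no safety endpoint, and the SAP nowhere says that p above 0.05 will be reported as no difference. That is correct. The comparison is nonetheless a stated purpose, and the plan sets no other basis for judging it.

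Section 6.14.3.1 lets a compound-level safety standard supersede the listed analyses of special topics. That standard is not part of the documents, so it may change the final outputs for those topics.

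A low-power argument is about sample size, and an interval does not raise power. True. What the interval changes is that the imprecision becomes visible.

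Two stronger readings are tempting and should not be adopted. A reader might infer that 480 per arm misses most relevant differences in the events of special interest. The documents give neither rates nor a relevance threshold. Infections and injection-site reactions are on the list and may be common, and miss rates are low in several scenarios: 16% for 4% versus 1%, 13% for 6% versus 2%, 1% for 20% versus 10% and 9% for 35% versus 25%. A reader might also infer that laboratory comparisons get intervals while adverse events do not. The interval sentence in SAP section 6.1.3 follows the imputation rule used for efficacy and health outcomes, and section 6.14.5 names no interval, so only the contrast with efficacy is secure.

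**Conclusion.** The point holds in a limited form. Fisher's exact test is the only planned between-arm inference for treatment-emergent events, serious events, discontinuations due to adverse events and events of special interest, and no interval for the difference is planned. With 480 per arm, a doubling from a base of 3% or less has 6% to 56% power, so a non-significant result on such an event cannot be read as no difference. Doublings from 5% upward and 10-point differences in the common events examined have 81% to 99% power, so the limitation does not extend to them. Differences of 3 to 5 points in common events mostly fall short: 42% to 62% in the scenarios shown, with 5% versus 10% the exception. All of this rests on assumed event rates. The change is a cheap improvement in reporting.

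**What to change.** In SAP section 6.14 and Table RHCR.6.8, add the risk difference, ixekizumab minus guselkumab, with a two-sided 95% confidence interval. Do this for overall treatment-emergent events, serious events, events leading to treatment discontinuation and each category of special interest, but not for every preferred term.

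Name one method suited to sparse counts, for example Miettinen-Nurminen. The simple asymptotic interval used for the non-inferiority analysis should not be carried over: with no events in either arm its standard error is zero and the interval has no width, whereas Newcombe's interval for 0 versus 0 is −0.8 to +0.8 points.

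State that the comparative safety statement rests on these intervals, that they are not adjusted for multiplicity (consistent with SAP section 6.4), and that Fisher's p-value is descriptive. Add a sentence that the two can disagree at sparse counts, and align the compound-level safety standard so that it does not override the change.

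The cost is SAP wording and extra columns in existing tables, with no new data and no effect on design, alpha or conduct. The one downside is that wide intervals for rare events will be on view.

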## 8. Discontinuation Criteria

### 8.1. Discontinuation from Study drug

#### 8.1.1. *Permanent Discontinuation from Study drug*

Possible reasons leading to permanent discontinuation of study drug:

- **Subject Decision**
  - the patient requests to discontinue study drug.
- **Discontinuation due to a hepatic event or liver test abnormality.**
  - Patients who are discontinued from study drug due to a hepatic event or liver test abnormality should have additional hepatic safety data collected via CRF.

Discontinuation of the study drug for abnormal liver tests should be considered by the investigator when a patient meets one of the following conditions after consultation with the Lilly designated medical monitor:

- ALT or AST >8x ULN
- ALT or AST >5xULN for more than 2 weeks
- ALT or AST >3xULN and total bilirubin level (TBL) >2xULN or international normalized ratio (INR) >1.5
- ALT or AST >3xULN with the appearance of fatigue, nausea, vomiting, right upper-quadrant pain or tenderness, fever, rash, and/or eosinophilia (>5%)
- ALP >3xULN
- ALP >2.5xULN and TBL >2xULN
- ALP >2.5xULN with the appearance of fatigue, nausea, vomiting, right quadrant pain or tenderness, fever, rash, and/or eosinophilia (>5%)

In addition, patients will be discontinued from the study drug in the following circumstances:

- Neutrophil (segmented) counts (see safety monitoring for neutropenia Section 9.4.6.1):
  - <500 cells/ $\mu$ L
  - $\geq$ 500 and <1000 cells/ $\mu$ L (based on 2 test results; the second test performed within 1 week from knowledge of the initial result)
  - $\geq$ 1000 and <1500 cells/ $\mu$ L (based on 3 test results as specified in Section 9.4.6.1) AND an infection that is not fully resolved
- Total WBC count <2000 cells/ $\mu$ L
- Lymphocyte count <200 cells/ $\mu$ L
- Platelet count <50,000 cells/ $\mu$ L
- The patient experiences a severe AE, an SAE, or a clinically significant change in a laboratory value occurs that in the opinion of the investigator, merits the discontinuation

of the study drug and appropriate measures being taken. In this case, Lilly or its designee is to be notified immediately via email and the event is to be documented.

- Clinically significant systemic hypersensitivity reaction following SC administration of study drug that does not respond to symptomatic medication or results in clinical sequelae
- The patient becomes pregnant

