	
Elevations in hepatic laboratory tests (alanine aminotransferase [ALT], aspartate aminotransferase [AST], alkaline phosphatase [ALP], total bilirubin) using Performing Laboratory Reference Ranges are defined as:
 
 • Include scheduled visits, unscheduled visits, and repeat measurements. • ALT or AST: maximum post-baseline measurement ≥ 3 times (3\times), 5 times (5\times), 10 times (10\times), and 20 times (20\times) the Performing lab upper limit of normal (ULN) for all patients with a post-baseline value. • The analysis of 3\times ULN will contain 4 subsets: patients whose non-missing maximum baseline value is $\leq 1 \times$ ULN, $>1 \times$ ULN to $<3 \times$ ULN, $\geq 3 \times$ ULN, or missing. • The analysis of 5\times ULN will contain 5 subsets: patients whose non-missing maximum baseline value is $\leq 1 \times$ ULN, $>1 \times$ ULN to $<3 \times$ ULN, $\geq 3 \times$ ULN to $<5 \times$ ULN, $\geq 5 \times$ ULN, or missing. • The analysis of 10\times ULN will contain 6 subsets: patients whose non-missing maximum baseline value is $\leq 1 \times$ ULN, $>1 \times$ ULN to $<3 \times$ ULN, $\geq 3 \times$ ULN to $<5 \times$ ULN, $\geq 5 \times$ ULN to $<10 \times$ ULN, $\geq 10 \times$ ULN, or missing. • The analysis of 20\times ULN will contain 7 subsets: patients whose non-missing maximum baseline value is $\leq 1 \times$ ULN, $>1 \times$ ULN to $<3 \times$ ULN, $\geq 3 \times$ ULN to $<5 \times$ ULN, $\geq 5 \times$ ULN to $<10 \times$ ULN, $\geq 10 \times$ ULN to $<20 \times$ ULN, $\geq 20 \times$ ULN, or missing. • Total bilirubin: maximum post-baseline measurement ≥ 1.5 times (1.5\times) and ≥ 2 times (2\times) the Performing lab ULN for all patients with a post-baseline value 
 ○ The analysis of 1.5\times ULN will contain 4 subsets: patients whose non-missing maximum baseline value is $\leq 1 \times$ ULN, $>1 \times$ ULN to $<1.5 \times$ ULN, $\geq 1.5 \times$ ULN, or missing. ○ The analysis of 2\times ULN will contain 5 subsets: patients whose non-missing maximum baseline value is $\leq 1 \times$ ULN, $>1 \times$ ULN to $<1.5 \times$ ULN, $\geq 1.5 \times$ ULN to $<2 \times$ ULN, $\geq 2 \times$ ULN, or missing. 	
Blinded Treatment Periods (Fisher’s exact test): Elevations in hepatic laboratory tests: maximum baseline category to abnormal maximum post-baseline category
 
Post-Treatment Follow-Up Period (Summary): Elevations in hepatic laboratory tests: maximum baseline category to abnormal maximum post-baseline category

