
	
ULN, or missing.
 
 Alkaline phosphatase (ALP): maximum post-baseline measurement >1.5 times (1.5×) the Performing lab ULN for all patients with a post-baseline value, and divided into 4 subsets: patients whose non-missing maximum baseline value is ≤1× ULN, >1× ULN to ≤1.5× ULN, >1.5× ULN, or missing. The number and percentages of patients meeting the following elevated hepatic criteria: maximum ALT ≥ 3× ULN and maximum Total Bilirubin ≥2× ULN during the treatment period will be summarized. 	
	
Shift for ALT, AST, and total bilirubin from maximum baseline to maximum post-baseline will be produced with the requirements using Performing Laboratory Reference Ranges:
 
 Include scheduled visits, unscheduled visits, and repeat measurements. Use the maximum non-missing value in the baseline period. Use the maximum non-missing post-baseline value within each study period. Categories are: 
 ALT: ≤1× ULN, >1 to <3× ULN, ≥3 to <5× ULN, ≥5 to <10× ULN, ≥10 to <20× ULN, and ≥20× ULN AST: ≤1× ULN, >1 to <3× ULN, ≥3 to <5× ULN, ≥5 to <10× ULN, ≥10× to <20× ULN and ≥20× ULN Total bilirubin: ≤1× ULN, >1 to <1.5× ULN, ≥1.5 to <2× ULN, ≥2× ULN ALP; ≤1× ULN, >1 to ≤1.5× ULN, >1.5× ULN With additional categories: 
 Decreased: post-baseline category < baseline category Increased: post-baseline category > baseline category Same: post-baseline category = baseline category 	
Blinded Treatment Periods (Summary): Shifts from maximum baseline to maximum post-baseline category
 
Post-Treatment Follow-Up Period (Summary): Shifts from maximum baseline to maximum post-baseline category

	
Evaluation of Drug-Induced Serious Hepatotoxicity (eDISH) plot: Each patient with at least one post-baseline ALT and total bilirubin contributes one point to the plot. The maximum ALT measurement and the maximum total bilirubin measurement after the first injection will be included. Patients will be classified into 2 groups: never on ixekizumab or ever on ixekizumab. The measurements do not need to be taken at the same blood draw. There will only be 1 eDISH plot for each indication regardless of treatment periods.
	
eDISH plot

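### The SAP's combined transaminase–bilirubin count uses ALT alone, so an AST-led case is left out of that count by arm; adding an ALT-or-AST row is a cheap improvement

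*SAP*

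**What the plan says.** SAP Section 6.14.3.1, Table RHCR.6.8, sets out the hepatic laboratory outputs.

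- Single-analyte elevations cover both transaminases: "ALT or AST: maximum post-baseline measurement ≥ 3 times" the ULN, and likewise 5×, 10× and 20×. Total bilirubin is counted separately at ≥1.5× and ≥2× ULN.
- One combined criterion follows: the number and percentage of patients with "maximum ALT ≥ 3× ULN and maximum Total Bilirubin ≥2× ULN during the treatment period".
- Shift tables run from maximum baseline to maximum post-baseline category, one analyte at a time, and include AST.
- The eDISH plot has one point per patient: "The maximum ALT measurement and the maximum total bilirubin measurement after the first injection will be included". AST is not plotted.

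SAP Section 6.14.5 adds a by-patient listing of abnormal hepatic results, using the shift-table categories other than normal.

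Protocol Section 8.1.1 lists liver-test conditions, one of which is "ALT or AST >3xULN and total bilirubin level (TBL) >2xULN or international normalized ratio (INR) >1.5". The list is introduced as advice: "Discontinuation of the study drug for abnormal liver tests should be considered by the investigator", after consultation with the sponsor's medical monitor. Protocol Section 9.2.1.2 names AST beside ALT, bilirubin and ALP in the liver adverse event of special interest.

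**The concern.** A combined count tells the reader how many patients in each arm had a transaminase rise and a bilirubin rise together. Separate tables for each analyte cannot give that number, because they do not show whether the two rises belong to the same patient.

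The SAP accepts either transaminase at 3× ULN when it looks at transaminases alone, but only ALT once bilirubin is added. Neither document gives a reason. A study report could therefore describe a patient considered for discontinuation under the AST part of Section 8.1.1 while the combined count for that arm reads zero. With a count at or near zero, one patient is visible in the table.

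**Working it through.** The plan states no figure here that could be reproduced. The check is logical: apply each rule to the same patient profiles and see where they part. All values are multiples of ULN, read as each patient's highest post-baseline values; TBL is total bilirubin.

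- Protocol Section 8.1.1, bilirubin limb: (ALT > 3 or AST > 3) and TBL > 2. The alternative limb, INR > 1.5, is set aside here.
- SAP combined count: ALT ≥ 3 and TBL ≥ 2.
- Wider count: (ALT ≥ 3 or AST ≥ 3) and TBL ≥ 2.

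| ALT | AST | TBL | Protocol condition | SAP count | Wider count |
|---|---|---|---|---|---|
| 4 | 4 | 2.5 | met | yes | yes |
| 4 | 2 | 2.5 | met | yes | yes |
| 2.5 | 4 | 2.5 | met | **no** | yes |
| 2.9 | 8.5 | 2.5 | met | **no** | yes |
| 3.0 | 2 | 2.0 | not met | yes | yes |
| 2.5 | 4 | 1.5 | not met | no | no |

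Rows 3 and 4 are the gap: AST ≥ 3, ALT < 3 and TBL ≥ 2. Row 5 shows the opposite difference, which arises because the protocol uses > and the SAP uses ≥. Every patient in the SAP count is also in the wider count, so widening can only add patients.

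The row 3 patient in the planned outputs:

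- AST table: counted at ≥3×.
- Bilirubin table: counted at ≥1.5× and ≥2×.
- Shift tables: AST in the 3 to <5 category, bilirubin in the ≥2 category, ALT in the >1 to <3 category.
- By-patient listing: all three abnormal results, under one patient.
- eDISH plot: a point at ALT 2.5 and bilirubin 2.5.
- Combined count by arm: absent.

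Size. The documents give no rate of AST-led joint elevations. Purely as an assumption, let the rate per patient be p. With 480 patients per arm the expected number is 480p, and the chance of at least one is 1 − (1 − p)^480. For p = 0.05%, 0.1%, 0.2% and 0.5% the expected numbers are 0.24, 0.48, 0.96 and 2.4, and the chances are 21%, 38%, 62% and 91%. The range is arbitrary and shows only how the answer depends on an unknown rate.

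Scheduled post-baseline chemistry falls at Week 12 and at Week 24 or the early termination visit. The SAP also takes in unscheduled and repeat measurements for these outputs.

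**The case against.** The strongest case against has four parts.

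1. Section 8.1.1 is a prompt to consider stopping study drug, not an analysis definition, and nothing obliges the SAP to tabulate it. Other protocol liver rules use ALT as the transaminase threshold: repeat testing at ≥3× ULN (Section 9.4.6.2) and extra data collection at ≥5× ULN on consecutive tests (Section 9.4.6.2.1). This stands. A reader might infer that the SAP contradicts the protocol; the documents do not support that, because the two rules serve different purposes. They also differ in the INR limb and in > against ≥, and adding AST would remove neither difference.

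2. The case is visible elsewhere. This also stands. A reader might infer that an AST-led case goes unseen, but the by-patient listing would show both rises in one patient. Bilirubin at ≥2× ULN also prompts repeat testing that includes AST, and extra hepatic data collection except in known Gilbert's syndrome. The listing still gives no number or percentage by arm, and someone must read across it to find the pair.

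3. On the eDISH plot a reader might infer that the patient drops below an ALT cut-off. The SAP states no threshold or reference line for that plot, and the patient is still plotted.

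4. SAP Section 6.14.3.1 lets a compound-level safety standard supersede it on special safety topics. That standard may already hold an AST-based count. It is not among the documents, so this can be neither confirmed nor ruled out.

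**Conclusion.** The point holds in a limited form. No planned table counts AST jointly with bilirubin, so a patient with AST ≥3×, ALT <3× and bilirubin ≥2× ULN is missing from the combined count and percentage by arm. The plan uses ALT or AST both in its single-analyte row and in the protocol's only joint transaminase–bilirubin condition, and does not explain the narrower choice.

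The size is at most one incomplete summary row. How many patients it would affect cannot be computed from the documents, and no efficacy result or treatment comparison is shown to change. The conclusion rests on the SAP text as it stands and assumes that the compound-level standard adds no such count. Severity: minor, a cheap improvement.

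**What to change.** In the hepatic section of SAP Table RHCR.6.8, keep the ALT-based row and add a second row, by treatment group and for the same period: maximum ALT or AST ≥3× ULN and maximum total bilirubin ≥2× ULN. If ALT alone is intended, or if the compound-level standard already supplies the wider count, say so in the SAP. An AST panel beside the eDISH plot is optional; the existing ALT axis need not be replaced.

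The cost is a line of SAP text and a small programming change. AST is already in the serum chemistry panel. The downside is that some AST rises of non-liver origin, such as muscle, may be counted and need review against CPK, which the same panel measures. Keeping the ALT row preserves the count as now planned. The change is to the analysis only; no discontinuation, monitoring or other clinical rule is altered.
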